Appendix 16. SBQ-R – Suicide Behaviors Questionnaire – Revised

Protocol ID: _____

CENTER				SUBJECT ID										

DATE OF VISIT

		-				-					
dd			MMM				yyyy				

Visit: _____

SUICIDAL BEHAVIORS QUESTIONNAIRE-REVISED (SBQ-R)

(1) NOT DONE Language administered: (44) English for USA

Instructions: Please check the number beside the statement or phrase that best applies to you.

1. Have you ever thought about or attempted to kill yourself? (check one only)

- 1. Never
- 2. It was just a brief passing thought
- 3a. I have had a plan at least once to kill myself but did not try to do it
- 3b. I have had a plan at least once to kill myself and really wanted to die
- 4a. I have attempted to kill myself, but did not want to die
- 4b. I have attempted to kill myself, and really hoped to die

2. How often have you thought about killing yourself in the past year? (check one only)

- 1. Never
- 2. Rarely (1 time)
- 3. Sometimes (2 times)
- 4. Often (3-4 times)
- 5. Very Often (5 or more times)

3. Have you ever told someone that you were going to commit suicide or that you might do it? (check one only)

- 1. No
- 2a. Yes, at one time, but did not really want to die
- 2b. Yes, at one time, and really wanted to die
- 3a. Yes, more than once, but did not want to do it
- 3b. Yes, more than once, and really wanted to do it

4. How likely is it that you will attempt suicide someday? (check one only)

- | | |
|--|---|
|  0. Never |  4. Likely |
|  1. No chance at all |  5. Rather likely |
|  2. Rather unlikely |  6. Very likely |
|  3. Unlikely | |

© Osman et al (1999) Revised. Permission for use granted by A. Osman, MD

Appendix 17. Patient Health Questionnaire – 8 Items

Protocol ID: _____

CENTER

SUBJECT ID

DATE OF VISIT

- -

dd MMM yyyy

Visit: _____

PATIENT HEALTH QUESTIONNAIRE (PHQ-8)

(1) NOT DONE Language Administered: (44) English for USA

Over the last 2 weeks , how often have you been bothered by the following problems?	Not at all (0)	Several days (1)	More than half the days (2)	Nearly every day (3)
1. Little interest or pleasure in doing things?				
2. Feeling down, depressed, or hopeless?				
3. Trouble falling or staying asleep, or sleeping too much?				
4. Feeling tired or having little energy?				
5. Poor appetite or overeating?				
6. Feeling bad about yourself—or that you are a failure or have let yourself or your family down?				
7. Trouble concentrating on things, such as reading the newspaper or watching television?				
8. Moving or speaking so slowly that other people could have noticed? Or the opposite—being so fidgety or restless that you have been moving around a lot more than usual?				

PHQ-8 is adapted from PRIME MD TODAY, developed by Drs Robert L. Spitzer, Janet B.W. Williams, Kurt Kroenke, and colleagues, with an educational grant from Pfizer Inc. For research information, contact [name] at [contact]. Use of the PHQ-8 may only be made in accordance with the Terms of Use available of <http://www.pfizer.com>. Copyright ©1999 Pfizer Inc. All rights reserved. PRIME MD TODAY is a trademark of Pfizer Inc.

090177e1912f28afApproved\Approved On: 26-Jun-2019 09:23 (GMT)

1. VERSION HISTORY

This is the third amendment of the Statistical Analysis Plan (SAP) for Study B7451012 and is based on Amendment 5 of the protocol dated 05JUN2018.

Table 1. Summary of Changes

Version/ Date	Associated Protocol Amendment	Rationale	Specific Changes
1 19 Feb 2018	Amendment 1 03 Nov 2017	N/A	N/A
2 22 Jun 2018	Amendment 3 16 Mar 2018	Clarification or completion of prior version	
Added change from baseline in total EASI score and SCORAD score, respectively as endpoints in Section 3.2.3.
 
Added responder analyses based on PtGA, HADS, DLQI / CDLQI and POEM as endpoints in Section 3.3.1.
 
Updated the definition of TEAE in Section 3.5.1.
 
Added text to include analyses for comparing active dose groups to Sections 5.2.1 through 5.2.4 and Section 6.
 
Removed references to the word “peak” in describing pruritus throughout the document.
 
Added further detail on the Efficacy Assessments and PROs within Appendices 4 and 6 through 8.
 
Additional minor changes to improve clarity and alignment with the protocol.

3 29 Mar 2019	Amendment 5 05 Jun 2018	Blinded data review / Regulatory (FDA) Input	
Replaced jump to reference analysis with a tipping point analysis, which is a more general approach and includes jump to reference as a special case. See sections 5.3.1, 6.1.2, 6.2.2 and Appendix 3.
 
Added an additional analysis option for handling binary missing data in Section 5.3.1. Updated the analysis of the NRS4 endpoint as regards handling of missing data in Sections 6.3.1 and 6.4.1 to account for a technical error in the process of transmission and collection of electronic data with the device that led to the NRS data not being collected across several sites.
 
Added a responder endpoint based on recently published data on the PSAAD in Section 3.3.1.

090177e1912f28b6\Approved\Approved On: 26-Jun-2019 09:22 (GMT)

			
Removed (with justification) from Sections 3.3.1 and 6.5, all references to the endpoint based on frequency of pruritus as based on the NRS.
 
Removed responder analysis based on POEM as an endpoint in Section 3.3.1.
 
Updated the definition of a treatment emergent adverse event (TEAE) in Section 3.5.1, in alignment with the latest CaPS algorithm.
 
Additional minor changes to improve clarity and alignment with the protocol.

4 23 Apr 2019	Amendment 5 05 Jun 2018	Clarification or completion of prior version	
Updated the visit windows in Appendix 2 to remove any gaps in the study period.
 
Further clarified the definition for non-responder imputation and imputation strategy when there are too few missing observations in Section 5.3.1.
 
Updated the criteria for inclusion into the PPAS in Section 4.2.

2. INTRODUCTION

This SAP provides the detailed methodology for summary and statistical analyses of the data collected in Study B7451012. This document may modify the plans outlined in the protocol; however, any major modifications of the primary endpoint definition or its analysis will also be reflected in a protocol amendment.

2.1. Study Objectives

Study objectives and corresponding endpoints are provided in the Table 2 below.

Table 2 Study Objectives and Endpoints

Primary Objective:
 
To assess the efficacy of PF-04965842 compared with placebo in subjects aged 12 years and older with moderate to severe Atopic dermatitis (AD).
	
Primary Endpoints:
 
The following co-primary endpoints will be tested:
 
 • Response based on the Investigator’s Global Assessment (IGA) score of clear (0) or almost clear (1) (on a 5-point scale); and a reduction from baseline of ≥ 2 points at Week 12. The baseline will be defined as the IGA score on Day 1 pre-dose. • Response based on the Eczema Area and Severity Index $\geq 75\%$ improvement from baseline (EASI-75) at Week 12. The baseline will be defined as the EASI score on Day 1 pre-dose.

Secondary Objectives:
 
To evaluate the effect of PF-04965842 on additional efficacy endpoints and patient reported outcomes over time in subjects aged 12 years and older with moderate to severe atopic dermatitis.
	
Secondary Endpoints:
 
Key Secondary Endpoints:
 
 • Response based on a ≥ 4 points of improvement in the numerical rating scale (NRS) for severity of pruritus from baseline at Weeks 2, 4, and 12. • Change from Baseline in Pruritus and Symptoms Assessment for Atopic Dermatitis (PSAAD) at Week 12. 
Secondary Efficacy Endpoints:
 
 • Response based on a ≥ 4 points of improvement in the numerical rating scale (NRS) for severity of pruritus from baseline at Week 8. • Time to achieve a ≥ 4-point improvement in the numerical rating scale (NRS) for severity of pruritus from baseline. • Response based on the EASI-75 at all scheduled time points except Week 12. • Response based on the IGA for clear (0) or almost clear (1); and ≥ 2 points reduction from baseline at all scheduled time points except Week 12. 
Other Efficacy Endpoints
 
 • Response based on a $\geq 50\%$ and $\geq 90\%$ improvement in the EASI total score (EASI-50 and EASI-90) at all scheduled time points. • Change from baseline in the percentage Body Surface Area (BSA) affected at all scheduled time points. • Response based on a $\geq 50\%$ and $\geq 75\%$ improvement in Scoring Atopic Dermatitis (SCORAD50, SCORAD75) from baseline at all scheduled time points. • Change from baseline at all scheduled time points in SCORAD subjective Visual Analogue Scale (VAS) assessments of itch and sleep loss. 
Additional Patient-reported Outcomes:
 
 • Change from baseline at Week 12 in Dermatology Life Quality Index (DLQI) or Children’s DLQI (CDLQI) and at all other scheduled time points. • Change from baseline at Week 12 in Hospital Anxiety and Depression Scale (HADS)

090177e1912f28b6\Approved\Approved On: 26-Jun-2019 09:22 (GMT)

[figure not shown]
	
and at all other scheduled time points.
 
 • Change from baseline at Week 12 in Patient-Oriented Eczema Measure (POEM) and at all other scheduled time points. • Change from baseline of Patient Global Assessment (PtGA) at Week 12 and at all other scheduled time points. • Change from baseline of EuroQol Quality of Life 5-Dimension 5-Level Scale (EQ-5D-5L) or EuroQol Quality of Life 5-Dimension Youth Scale (EQ-5D-Y) at Week 12 and at all other scheduled time points. • Change from baseline of Functional Assessment of Chronic Illness Therapy Fatigue Scale (FACIT-F) or Pediatric FACIT-F (Peds-FACIT-F) at Week 12 and at all other scheduled time points. • Change from baseline of Short Form-36 (SF-36), acute at Week 12 and at all other scheduled time points. • Response based on at least 4 points improvement in the frequency of pruritus numerical rating scale (NRS) from baseline at all scheduled time points.¹ • Time from baseline to achieve at least 4 points improvement in the frequency of pruritus NRS scale.¹
Safety Objective	Safety Endpoints
To evaluate the safety and tolerability of PF-04965842 in subjects aged 12 years and older with moderate to severe atopic dermatitis following 12 weeks of treatment.	
 • Incidence of Treatment Emergent Adverse Events (TEAEs). • Incidence of Serious Adverse Events (SAEs) and Adverse Events (AEs) leading to discontinuation. • The incidence of clinical abnormalities and change from baseline in clinical laboratory values, Electrocardiogram (ECG) measurements, and vital signs.
PK Objectives	PK Endpoint
To evaluate the pharmacokinetics (PK) of PF-04965842 in subjects aged 12 years and older with moderate to severe atopic dermatitis following 12 weeks of treatment.	
 • Population PK characterization in subjects aged 12 years old and above with moderate to severe atopic dermatitis.

¹ The frequency of pruritus numerical rating scale (NRS) is listed as an endpoint in the protocol but will not be analyzed. This is because, after its selection as an endpoint in the study protocol, evidence was uncovered that suggested the instrument did not have sufficient content validity. Specifically, the response scale for the frequency of pruritus NRS was found not to be ideally representative of the range of frequency levels from the perspective of the target population based on qualitative research. Data generated from this measure would not be easily interpretable. Therefore, the endpoint has been removed from this SAP.

2.2. Study Design

This is a randomized, double-blind, placebo-controlled, parallel-group, Phase 3 study to evaluate the efficacy and safety of PF-04965842 monotherapy in subjects aged 12 years and older with moderate to severe AD and a body weight ≥ 40 kg. The treatment duration is 12 weeks. Subjects will be screened within 28 days prior to the first dose of investigational product to confirm that they meet the subject selection criteria for the study. A total of approximately 375 subjects will be enrolled from approximately 75 sites located globally. A study design schematic is presented in Figure 1.

Figure 1 Study Design Schematic

* At Week 12, eligible subjects may enter a long-term extension study; all other subjects enter the 4 week follow-up period

Qualified subjects completing the 12-week treatment period of the study will have the option to enter a long-term extension (LTE) study B7451015. Subjects discontinuing early from treatment, or who are otherwise ineligible for the LTE study, will undergo a 4-week follow-up period in B7451012.

Subjects who have chronic moderate to severe AD as defined per the inclusion criteria and have a documented history of inadequate response or intolerance to treatment with topical AD medications will be randomized in a 2:2:1 ratio to receive 200 mg PF-04965842 (N=150) or 100 mg PF-04965842 QD (N=150), or matching placebo (N=75) from Day 1. Randomization will be stratified by baseline disease severity (moderate [IGA=3] and severe [IGA=4] AD) and age (age < 18 and ≥ 18 years). Investigators, subjects, and the sponsor study team will be blinded as to treatment group.

A full schedule of activities for the study is provided in [Appendix 9](#).

Study Treatments

- Doses of PF-04965842 will be 200 mg or 100 mg taken QD orally, or matching placebo;

- Treatment duration will be 12 weeks;

Sample Size Determination

Sample size for the study was based on the co-primary endpoints. A sample of 150 subjects randomized to PF-04965842 200 mg QD, 150 subjects randomized to PF-04965842 100 mg QD and 75 subjects randomized to placebo would provide at least 95% power to detect a difference in IGA response rate of at least 20% between PF-04965842 200 mg QD (or PF-04965842 100 mg QD) and placebo, assuming the placebo response rate is 6% at Week 12. Furthermore, this will also provide at least 99% power to detect a difference in EASI-75 response rate of at least 30% between PF-04965842 200 mg QD (or PF-04965842 100 mg QD) and placebo, assuming the placebo response rate is 15% at Week 12.

The Type-I error for testing each individual co-primary endpoint was set at 5%. Since both endpoints are co-primary, the study will meet its primary endpoint only if both hypotheses (corresponding to each co-primary endpoint) are rejected. Therefore, the Type-I error rate remains controlled at 5% for testing the primary endpoints. The power to reject both hypotheses when a true difference exists (alternative hypothesis is true) could be at least 94% depending on the correlation between the endpoints.

3. ENDPOINTS AND BASELINE VARIABLES: DEFINITIONS AND CONVENTIONS

3.1. Primary Endpoints

The co-primary efficacy endpoints are:

- Response based on the IGA score of clear (0) or almost clear (1); and a reduction from baseline of ≥ 2 points at Week 12;
- Response based on the EASI $\geq 75\%$ improvement from baseline (EASI-75) at Week 12.

Detailed descriptions of how the IGA and the EASI scores are derived are provided in [Appendix 4](#) and [Appendix 5](#) respectively.

3.2. Key Secondary Endpoints

The key secondary efficacy endpoints are:

- Response based on ≥ 4 points improvement from baseline in the pruritus NRS (NRS4) for severity at Weeks 2, 4 and 12;
- Change from baseline in PSAAD score at Week 12.

Detailed descriptions of how the pruritus NRS and the PSAAD scores are derived are provided in [Appendix 7](#) and [Appendix 8](#) respectively.

3.3. Secondary Efficacy Endpoints

The secondary efficacy endpoints are:

- Response based on the EASI-75 at all scheduled time points except Week 12;
- Response based on the IGA for clear (0) or almost clear (1); and ≥ 2 points reduction from baseline at all scheduled time points except Week 12;
- Response based on the IGA for clear (0) at all scheduled time points;
- Response based on a $\geq 50\%$, $\geq 90\%$ and 100% improvement in the EASI total score (EASI-50, EASI-90 and EASI-100) at all scheduled time points;
- Change from baseline at all scheduled time points in the EASI total score;
- Change from baseline in %BSA (from EASI) affected at all scheduled time points;
- Response based on achieving percent BSA $< 5\%$;
- Response based on a $\geq 50\%$ and $\geq 75\%$ improvement in SCORAD (SCORAD50, SCORAD75) from baseline at all scheduled time points. A detailed description of the derivation of the SCORAD score is provided in [Appendix 6](#);
- Change from baseline at all scheduled time points in the SCORAD total score;
- Change from baseline at all scheduled time points in SCORAD subjective VAS assessments of sleep loss.

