Endpoints

Primary Endpoints:

- Response based on the Investigator's Global Assessment (IGA) score of clear (0) or almost clear (1) (on a 5-point scale) and a reduction from baseline of ≥ 2 points at Week 12. The baseline will be defined as the IGA score on Day 1 pre-dose;
- Response based on the Eczema Area and Severity Index 75% improvement from baseline (EASI-75) response at Week 12. The baseline will be defined as the EASI score on Day 1 pre-dose.

Key Secondary Efficacy Endpoints:

- Response based on at least 4 points improvement in the severity of pruritus numerical rating scale (NRS) from baseline at Weeks 2, 4, and 12;
- Change from Baseline in Pruritus and Symptoms Assessment for Atopic Dermatitis (PSAAD) total score at Week 12.

Secondary Efficacy Endpoints:

- Response based on at least 4 points improvement in the severity of pruritus numerical rating scale (NRS) from baseline at all scheduled time points other than Weeks 2, 4 and 12;
- Time from baseline to achieve at least 4 points improvement in the severity of pruritus NRS scale;
- Response based on the EASI-75 at all scheduled time points except Week 12;
- Response based on the IGA of clear (0) or almost clear (1) and ≥ 2 point reduction from baseline at all scheduled time points except Week 12.

Other Efficacy Endpoints:

- Response based on a $\geq 50\%$ and $\geq 90\%$ improvement in the EASI total score (EASI-50 and EASI-90) at all scheduled time points;
- Change from baseline in the percentage Body Surface Area (BSA) affected at all scheduled time points;
- Response based on a $\geq 50\%$ and $\geq 75\%$ improvement in Scoring Atopic Dermatitis (SCORAD) (SCORAD-50, SCORAD-75) from baseline at all scheduled time points;
- Change from baseline at all scheduled time points in SCORAD-subjective assessments of itch and sleep loss.

Patient-Reported Outcomes:

- Change from baseline at Week 12 in Dermatology Life Quality Index (DLQI) or Children's DLQI (CDLQI) and at all other scheduled time points;
- Change from baseline at Week 12 in Hospital Anxiety and Depression Scale (HADS) and at all other scheduled time points;
- Change from baseline at Week 12 in Patient-Oriented Eczema Measure (POEM) and at all other scheduled time points;
- Change from baseline of Patient Global Assessment (PtGA) at Week 12 and at all other scheduled time points;

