
Secondary Objective: To evaluate the effect of PF-04965842 on additional efficacy endpoints and patient reported outcomes over time in subjects aged 12 years and older with moderate to severe atopic dermatitis.
	
Secondary Endpoints:
 
Key Secondary Endpoints:
 
 • Response based on at least 4 points improvement in the severity of pruritus numerical rating scale (NRS) from baseline at Weeks 2, 4, and 12; • Change from Baseline in Pruritus and Symptoms Assessment for Atopic Dermatitis (PSAAD) total score at Week 12. 
Secondary Efficacy Endpoints:
 
 • Response based on at least 4 points improvement in the severity of pruritus numerical rating scale (NRS) from baseline at all scheduled time points other than Weeks 2, 4 and 12; • Time from baseline to achieve at least 4 points improvement in the severity of pruritus NRS scale; • Response based on the EASI-75 at all scheduled time points except Week 12; • Response based on the IGA of clear (0) or almost clear (1) and ≥ 2 point reduction from baseline at all scheduled time points except Week 12. 
Other Efficacy Endpoints:
 
 • Response based on a $\geq 50\%$ and $\geq 90\%$ improvement in the EASI total score (EASI-50 and EASI-90) at all scheduled time points; • Change from baseline in the percentage Body Surface Area (BSA) affected at all scheduled time points; • Response based on a $\geq 50\%$ and $\geq 75\%$ improvement in SCORAD (SCORAD50, SCORAD75) from baseline at all scheduled time points; • Change from baseline at all scheduled time points in SCORAD subjective assessments of itch and sleep loss. 
Patient-reported Outcomes:
 
 • Change from baseline at Week 12 in Dermatology Life Quality Index (DLQI) or Children’s DLQI (CDLQI) and at all other scheduled time points;

090177e1912f28afApproved\Approved On: 26-Jun-2019 09:23 (GMT)

Table 1. Objectives and Endpoints

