7.6.4. Scoring Atopic Dermatitis (SCORAD)

SCORAD is a validated scoring index for atopic dermatitis, which combines extent (0-100), severity (0-18), and subjective symptoms (0-20) based on pruritus and sleep loss, each scored (0-10).

Extent (A, maximum score of 100%)

To determine extent of AD, rule of 9 is used to calculate body surface area affected by AD as a percentage of the whole body surface area. Body surface area as percentage of total body surface area for each body region is as follows:

- Head and neck 9%;
- Upper limbs 9% each;
- Lower limbs 18% each;
- Anterior trunk 18%;
- Back 18%;
- 1% for genitals.

The score for each body region is added up to determine the BSA affected by AD (A), which has a possible maximum score of 100%.

Severity (B, maximum score of 18)

A representative area of AD is selected. In this area, the severity of each of the following signs is assessed as none (0), mild (1), moderate (2) or severe (3):

- Erythema (reddening);
- Edema (swelling)/papulation;
- Oozing/crusting;
- Excoriation (scratch marks);
- Skin thickening (lichenification);
- Xerosis (dryness) (this is assessed in an area where there is no inflammation).

The severity scores are added together to give 'B' (maximum score of 18).

Subjective Symptoms (C, maximum score of 20)

Subjective symptoms (ie, itch and sleep loss) are each scored by the subject using a visual analog scale (VAS) where “0” is no itch (or no sleep loss) and “10” is the worst imaginable itch (or sleep loss). The value for each should reflect the average on a 10 point scale for the last 3 days/nights. These scores are added to give 'C' (maximum score of 20).

SCORAD Total Score

The SCORAD for an individual is calculated by the formula: $A/5 + 7B/2 + C$ (can range from 0 to 103).

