This imputation will be repeated multiple times with different MCMC samples to obtain multiple completed datasets. For each such completed dataset, the estimates of the proportions and CMH-weighted difference of proportions between each PF-04965842 dose group and placebo will be obtained along with the associated standard errors using the methods in [Section 5.2.1](#). Rubin’s rule (Rubin, 1987) will be used to combine the multiple estimates and standard errors across the imputed datasets and provide p-values.

The above analysis can be repeated for different combinations of MNAR quantities which will be applied to the probability of response to assess when the conclusion might change (i.e., tipping). Two important scenarios are included in the tipping point analysis framework. When the MNAR quantities are zero and the posterior predictive probabilities in the PF-04965842 dose groups are not shifted, results are obtained under an assumption of MAR for the missing data mechanism. Alternatively, at the other extreme, when the MNAR quantities are 1.0 for each PF-04965842 dose group, results are obtained under an assumption that the distribution of the missing responses after discontinuation of either dose of PF-04965842 is the same as that of the missing responses on the placebo arm. More detailed descriptions are provided in [Appendix 3](#).

Due to a technical error in the process of transmission and collection of electronic data with the device, the data on the pruritus NRS scale was not collected from several subjects at the scheduled visits of Week 2 (Day 15) and after. This was not restricted to a particular site or country and was not indicative of being related to the missing value of pruritus endpoint or any other endpoints. As such, the missing data mechanism may be reasonably assumed to be missing completely at random or missing at random.

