6.4.5. Weeks 2, 4 and 8 EASI-75 Response

- Summary: Proportion of subjects with Weeks 2, 4 and 8 EASI-75 response;
- Population: FAS;
- Statistical Method: CMH and normal approximation in [Section 5.2.1](#);
- Missing Data: Missing data arising due to subject dropout are considered “non-response” (see [Section 5.3.1](#)).

6.4.6. Weeks 2, 4, 8 and 12 Change from Baseline in Total EASI Score, Total SCORAD Score, Severity of Pruritus NRS, %BSA, SCORAD (VAS) of Sleep Loss

- Summary: Change from baseline in Total EASI Score, Total SCORAD Score, Severity of Pruritus NRS, %BSA, SCORAD (VAS) of Sleep Loss at Weeks 2, 4, 8 and 12;

- Population: FAS;
- Statistical Method: MMRM in [Section 5.2.3](#);
- Missing Data: Observed Data.

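### The SCORAD itch VAS is a listed endpoint in the protocol and SAP Table 2, but the SAP's analysis sections cover only sleep loss and record no reason

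*SAP*

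**What the plan says.** Three places name both items. The Protocol Summary lists, among the Other efficacy endpoints, "Change from baseline at all scheduled time points in SCORAD-subjective assessments of itch and sleep loss". Protocol Section 2, Table 1 repeats it: "Change from baseline at all scheduled time points in SCORAD subjective assessments of itch and sleep loss". SAP Table 2 agrees: "Change from baseline at all scheduled time points in SCORAD subjective Visual Analogue Scale (VAS) assessments of itch and sleep loss".

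The sections that define and analyse the endpoint are narrower. SAP 3.3 has "Change from baseline at all scheduled time points in SCORAD subjective VAS assessments of sleep loss". SAP 6.4.6, which specifies the MMRM on the FAS, ends its list with "SCORAD (VAS) of Sleep Loss at Weeks 2, 4, 8 and 12". The corresponding row of Appendix 1 also names sleep loss only.

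Protocol 7.6.4 and SAP Appendix 6 describe itch and sleep loss as two separate subject-scored visual analogue items, each from 0 to 10, referring to the average over the last three days and nights. The Schedule of Activities has SCORAD at screening, baseline, Weeks 2, 4, 8 and 12, and follow-up.

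**The concern.** The SAP disagrees with the protocol and with its own Table 2 on what will be analysed. SAP Section 2 allows the SAP to modify the protocol's plan, so dropping an Other endpoint is permissible. It should be visible, though, and the SAP shows how that is done: the pruritus-frequency NRS has a footnote to Table 2 with a rationale and an entry in the version history. The SCORAD itch item has neither, so a reader cannot tell a decision from a drafting slip.

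At stake is completeness of reporting. A listed patient-scored itch endpoint would be absent from the results without explanation, in a trial where itch is a key secondary outcome. That invites a question about selective reporting which is easily avoided.

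**Working it through.** No plan figure has to be reproduced. The check is a comparison of every place where the SCORAD subjective items are listed, defined or analysed.

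| Place | Itch VAS | Sleep-loss VAS |
|---|---|---|
| Protocol Summary, Other efficacy endpoints | listed | listed |
| Protocol Section 2, Table 1 | listed | listed |
| SAP 2.1, Table 2 | listed | listed |
| SAP 3.3 | absent | defined |
| SAP 6.4.6 | absent | MMRM, FAS |
| SAP Appendix 1 | absent | MMRM, FAS |

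**Is itch picked up elsewhere?** SAP 3.3.1 and 6.5 hold the patient-reported outcomes. Neither includes the SCORAD itch VAS.

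**Is a reason given?** The Table 2 footnote is attached to the two pruritus-frequency rows only. The version history records the removal of the frequency NRS and of the POEM responder analysis, and says nothing of SCORAD itch. Its general entries about minor changes speak of aligning the SAP with the protocol. Dropping a protocol endpoint does the opposite, so those entries cannot cover it.

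**What is lost?** SAP 5.2.3 provides, for each MMRM endpoint, each dose against placebo at each visit and an estimate of 200 mg against 100 mg. For the itch VAS that is 2 × 4 = 8 placebo contrasts and 1 × 4 = 4 dose-against-dose estimates that would not be produced.

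**How much of the item survives in the total?** SCORAD is A/5 + 7B/2 + C. Its maximum is 100/5 + 7 × 18/2 + 20 = 20 + 63 + 20 = 103. Itch supplies at most 10 of the 20 points in C, so at most 10/103 = 9.7% of the total score range. Sleep loss has the same weight and keeps its own analysis. The total score therefore does not replace an item-level result for itch.

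**The case against.** Much of the case on the other side stands.

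- The item is classed as Other in the protocol and in SAP Table 2. It lies outside the sequential testing procedure, and any test would be at a nominal 5%.
- Itch remains well covered by NRS4, time to NRS4, change in the NRS for severity, and PSAAD.
- Appendix 1 is not exhaustive. It also omits the %BSA below 5% response planned in SAP 6.4.7, so its silence alone proves little. The weight rests on 3.3 and 6.4.6.
- A one-line footnote would cure the inconsistency as well as an added analysis would.

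A reader might also infer four stronger things, none of which the documents support.

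- *That itch was deliberately dropped.* Table 2 still lists it, and an omission in drafting fits equally well.
- *That the itch VAS is never used.* It still enters change in total SCORAD, SCORAD50 and SCORAD75.
- *That it is the only other single itch item.* PSAAD item 1, the pruritus-frequency NRS and the first POEM question are also single itch items, although the SAP plans no separate analysis of any of them.
- *That it is the natural check on NRS4.* The link is tempting because SAP 5.3.1 reports that "the data on the pruritus NRS scale was not collected from several subjects at the scheduled visits of Week 2 (Day 15) and after". But the SCORAD item asks for a three-day average and the NRS for the worst itch in 24 hours, and a mean change does not test a responder rate of at least 4 points. Protocol 7.7 assigns the NRS and PSAAD to the handheld device but does not say how the SCORAD VAS is captured, so its independence from the fault is an assumption. The SAP already addresses the lost NRS data by multiple imputation, with a sensitivity analysis that counts all missing data as non-response.

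**Conclusion.** The inconsistency is real and unexplained. Three places list itch and sleep loss, three define or analyse sleep loss only, and no text connects the two. As written, one of the two listed SCORAD subjective endpoints receives no stand-alone analysis at any of the four post-baseline visits.

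The consequence is limited. Type I error, power, and the primary and key secondary conclusions are unaffected. The point deserves correction because the SAP contradicts itself and the remedy is close to free, not because any main result depends on it. The conclusion rests on the text alone and needs no assumption about why itch was left out or how many NRS values were lost, which the SAP does not state.

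**What to change.** Add the SCORAD VAS of itch beside sleep loss in SAP 3.3, in the heading and summary of 6.4.6, and in the matching row of Appendix 1. Use the model already specified for sleep loss: the MMRM of SAP 5.2.3 on the FAS with observed data at Weeks 2, 4, 8 and 12. The item is already collected as part of SCORAD, so the cost is a few words and one more table.

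If removal was intended, footnote the row in Table 2 and give the reason in the version history, as was done for the frequency NRS. That costs two sentences.

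If the analysis is kept, describe it as additional descriptive evidence on itch. Mentioning it alongside the NRS device failure is reasonable, provided it is not presented as confirming NRS4.
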